4.12.1 Brief Summary of Adverse Events

The number (%) of subjects reporting any of the following events during study will be reported in the brief summary of AEs for the ITT and Safety populations:

- AE
- AE related to study drug use
- AE related to study drug placement/removal procedure
- SAE
- SAE related to study drug use
- SAE related to study drug placement/removal procedure

- AE leading to study drug removal
- AE leading to study discontinuation
- Death

4.12.2 Adverse Events by System Organ Class and Preferred Term

The incidence of AEs and SAE will be summarized by MedDRA primary SOC and PT. The summary will include the total number and percentage of subjects reporting an AE within an SOC and/or PT.

The incidence of AEs by SOC and PT for the Safety and ITT populations

The incidence of AEs by SOC and PT by maximum severity for the Safety population

The incidence of AEs by SOC and PT by closest relationship to study drug use for the Safety population

The incidence of AEs by SOC and PT by closest relationship to drug placement/removal procedure for the Safety and ITT populations

The incidence of SAEs by SOC and PT for the Safety and ITT populations

The incidence of SAEs by SOC and PT by maximum severity for the Safety population

The incidence of SAEs by SOC and PT by closest relationship to study drug use for the Safety population

The incidence of SAEs by SOC and PT by closest relationship to drug placement/removal procedure for the Safety and ITT populations

The incidence of AE leading to study drug removal by SOC and PT for the Safety population

The incidence of AE leading to study discontinuation by SOC and PT for the Safety population

Listing of AE leading to death for the ITT population

Incidence of AEs experienced by at least 5% of subjects by SOC and PT for the Safety population

Incidence of AESIs(e.g. pain during insertion, pelvic inflammatory disease, ectopic pregnancies, uterine perforations, expulsions, uterine perforation, dysmenorrhea, and abdominal pain) will be summarized for Safety and ITT populations.

4.12.3 Narratives of Deaths, Serious Adverse Events, and Other Significant Adverse Events

Narratives of deaths, SAEs, and other significant AEs will be provided in the relevant section of the clinical study report.

4.12.4 Adverse Event Listing

A complete subject listing of all AEs will be provided in Appendix 16.2 to the study report. This listing will include treatment, AE verbatim term, MedDRA primary SOC and PT, the time of onset and cessation of the event relative to the first insertion of study drug, duration of the AE, whether serious or not, severity, relationship to study drug, action taken, and outcome. Treatment-emergent and non-treatment-emergent events will be listed separately.

In addition, separate listings of all SAEs, AEs related to study drug, AEs related to study drug placement/removal procedure, AEs leading to death, AEs leading to study drug removal, and AEs as primary reason for exiting study will be provided.

4.12.5 Subgroup Analysis for Adverse Events

Tables of brief summary of AEs, AEs by SOC and PT, SAEs by SOC and PT, and AESIs will be presented by the following subgroup variables for the Safety population:

- Race group
- BMI group at enrollment
- Age group at enrollment
- Parity status at enrollment

4.12.6 Bleeding and Spotting Patterns

Bleeding and spotting patterns will be summarized (per Mishell [8]) for the ECYC population for the first year of treatment by the number of days (n, mean (SD), min, median, max) in each 28-day cycle with bleeding or spotting, bleeding only, and spotting only. Number (%) of subjects with amenorrhea (absence of menstruation) will also be reported by cycle. The analysis will be repeated by parity at enrollment.

Occurrence and intensity of vaginal bleeding and spotting will be recorded daily by subjects in e-diary. If there are more than 7 missing values in a cycle of 28 days, the cycle will not be used for this analysis. Single missing values will be imputed as the maximum bleeding intensity recorded on the day before and after the missing day. Last value of the previous cycle and the first value of the next cycle could be used for imputation for the single missing value in the current cycle. Two consecutive missing values will be imputed by carrying forward the last non-missing and carrying backward the next non-missing. Three or more consecutive missing will be left missing.

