8.1 Inclusion Criteria

Subjects must meet all of the following criteria to participate in this study:

- 1. Post-menarcheal, pre-menopausal females up to 45 years of age at the time of informed consent/assent and in good general health;
- 2. History of regular menstrual cycles defined as occurring every 21-35 days when not using hormones or prior to recent pregnancy or spontaneous or induced abortion;
- 3. Sexually active with a male partner who has not had a vasectomy;
- 4. Reasonably expect to have coitus at least once monthly during the study period;
- 5. In a mutually monogamous relationship of at least 3 months duration;
- 6. Seeking to avoid pregnancy for the duration of the study;
- 7. Willing to use the study drug as the sole form of contraception;
- 8. Willing to accept a risk of pregnancy;
- 9. Subjects must be in compliance with cervical cancer screening guidelines per the American Society for Colposcopy and Cervical Pathology (ASCCP) guidelines without evidence of disease. Subjects who are age 21-24 y/o, at time of informed consent, must have a normal Papanicolaou test (Pap), atypical squamous cells of undetermined significance (ASC-US), or low-grade squamous intraepithelial lesion (LSIL). Subjects who are 25 or older at the time of informed consent with ASC-US results, must also have a negative high-risk human papilloma virus (HPV) test result within the appropriate screen timeframe, and prior to study IUS insertion. Alternatively, the subject must have had a colposcopy performed within the appropriate screen timeframe per American Society for Colposcopy and Cervical Pathology (ASCCP) guidelines, and prior to study IUS insertion that showed no evidence of dysplasia requiring treatment per ASCCP guidelines, or treatment was performed and follow-up at least 6 months after the treatment showed no evidence of disease by clinical evaluation;
- 10. Able and willing to comply with all study tests, procedures, assessment tools (including e-diary), and follow-up;
- 11. Able and willing to provide and document informed consent and Authorization for Release of Protected Health Information (PHI). Unemancipated subjects under 18 years old must provide assent and have written parental consent documented on the consent form consistent with local legal requirements;
- 12. Plan to reside within a reasonable driving distance of a research site for the duration of the study;
- 13. Subject agrees not to self-remove VeraCept;

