12.3 VeraCept Placement/ Enrollment (Day 1)

VeraCept can be inserted on any day of the menstrual cycle using the first three criteria for the Centers for Disease Control and Prevention (CDC) U.S. Selected Practice Recommendations for Contraceptive Use, 2016 [1] as guidance to avoid an undetected pregnancy (see the revised Box 2 below from the CDC Selective Practice Recommendations and a copy is located in the study reference manual provided to the site).

Post Pregnancy Guidelines

Subjects who were recently pregnant must have a urine pregnancy test performed no sooner than 4 weeks post-pregnancy. If a subject has not had 2 normal menses since the end of a pregnancy, the study IUS may be placed if her hCG is negative and she has been on a reliable method of contraception (e.g., pills, patch, ring) that was started within 2 weeks post-pregnancy or has been on this reliable method for 4 weeks. If the urine hCG is still positive, investigators can obtain two quantitative hCG tests that must demonstrate declining hCG values at least 1 day apart.

BOX 2. How to be reasonably certain that a woman is not pregnant[1]

A health care provider can be reasonably certain that a woman is not pregnant if she has no symptoms or signs of pregnancy and meets any one of the following criteria:

- is ≤ 7 days after the start of normal menses
- has not had sexual intercourse since the start of last normal menses
- has been correctly and consistently using a reliable method of contraception*

Subjects must have a negative urine pregnancy test immediately prior to VeraCept placement. VeraCept insertion is consistent with standard IUS placement. Refer to the Clinician's Quick Guide and Investigator's Brochure for specific instructions.

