4.1.2 Reference Date and Study Day Calculation

A subject could have 2 study drug insertion attempts, which could be on different dates. The following 2 study reference dates will be defined to meet the analysis requirement specified in the protocol and this SAP.

- First study reference date=date of the first insertion attempt
- Second study reference date=date of successful insertion

The first study reference date will be used for Intent-to-Treat (ITT) analysis to include all data since first device insertion attempt regardless of insertion success or failure (e.g., AEs related to replacement procedure).

The second study reference date will be used to define exposure period and analysis visit windows for all cycle-based analysis and analysis for data with scheduled data collection.

The second study reference date is Day 1 of Cycle 1.

For both reference dates, study day will be calculated as follows:

If event date > study reference date:

Study day of event = Event date - Study reference date + 1

If event date < study reference date:

Study day of event = Event date – Study reference date

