4.1.5 Exposure Periods

The first exposure cycle starts on Day 1 of successful study drug insertion. A full exposure cycle is comprised of 28 days. One woman-year comprises thirteen 28-day cycles. The following exposure periods are defined for analysis in terms of planned study days and study cycles to facilitate the efficacy and certain safety analyses.

Exposure Period	Study Day of Period Start (PSTDY)	Study Day of Period End (PENDY)
Year 1 (Cycle 1- Cycle 13)	1	364
Year 2 (Cycle 14-Cycle 26)	365	728
Year 3 (Cycle 27-Cycle 39)	729	1092
Year 4 (Cycle 40-Cycle 52)	1093	1456
Year 5 (Cycle 53-Cycle 65)	1457	1820
First 2 Years (Cycle 1-Cycle 26)	1	728
First 3 Years (Cycle 1-Cycle 39)	1	1092
First 4 Years (Cycle 1-Cycle 52)	1	1456
5 Years (Cycle 1-Cycle 65)	1	1820

Type of Events and Study Day During an Exposure Period

ЕТҮРЕ	Event	Study Day of Event (EVTDY)		
A	Expulsion	Study Day of Expulsion date		
В	Expulsion followed by conception within 7 days	Study Day of Expulsion date		
С	Removal	Study Day of Removal date		
D	Removal followed by conception within 7 days	Study Day of Removal date		
Е	Pregnancy before expulsion	Study Day of Conception date		
F	Pregnancy before removal	Study Day of Conception date		
Н	Lost to follow-up without pregnancy, expulsion or removal	Study Day of Last Date Device in Situ.		
I	Complete period without pregnancy, expulsion or removal	Study Day of Period End Date		

Note: Removal due to partial expulsion will be treated as expulsion

Exposure Duration in Days (EXDUR):

if EVTDY-PSTDY>0 then EXDUR = min(EVTDY-PSTDY+1, PENDY-PSTDY+1); else EXDUR=.;

Exposure Duration in Cycles (NCYCF) = EXDUR/28

Number of Completed Cycles (NCYCC) = INT(NCYCF)

Number Relevant Cycles (NCYCR)

- =NCYCC+1 if last partial cycle is >=23 days
- =NCYCC+1 if last partial cycle ETYPE is B or D or E or F
- =NCYCC, otherwise.

Number of Cycles with back-up contraceptives (including emergency contraception) or no intercourse within the period or there is no diary data (NCYCEXCL):

Exclude from NCYCEXCL the cycle in which the subject had an on-treatment pregnancy (ETYPE is B, D, E, F).

Back-up contraceptives or intercourse history are recorded in subject's diary.

If there are missing values then they will be handled as follows:

Missing back-up contraceptive diary entries will be treated as no back-up contraceptive use.

Missing intercourse diary will be treated as no intercourse.

Number of Evaluable Cycles (NCYCEV) = NCYCR-NCYCEXCL

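### SAP 4.12.6 tabulates amenorrhea in fixed 28-day blocks while eligible cycles run to 35 days, so some regularly menstruating women can be counted as amenorrheic in some blocks

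*SAP*

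**What the plan says.** SAP 4.12.6 summarises bleeding and spotting for the first year in the ECYC population and adds: "Number (%) of subjects with amenorrhea (absence of menstruation) will also be reported by cycle". The parenthesis is the only definition of amenorrhea given. The section does not say whether spotting or intermenstrual bleeding counts against it.

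The word cycle has a fixed meaning in the SAP. Section 4.1.5 says "A full exposure cycle is comprised of 28 days" and "One woman-year comprises thirteen 28-day cycles". Section 4.1.2 starts the count at successful insertion ("The second study reference date is Day 1 of Cycle 1") and applies that anchor broadly: "The second study reference date will be used to define exposure period and analysis visit windows for all cycle-based analysis". The blocks are therefore not aligned to menses. Protocol 12.3 makes the offset arbitrary: "VeraCept can be inserted on any day of the menstrual cycle".

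On natural cycle length, criterion 2 of Protocol 8.1 requires "History of regular menstrual cycles defined as occurring every 21-35 days when not using hormones".

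For missing diary days, SAP 4.12.6 says "If there are more than 7 missing values in a cycle of 28 days, the cycle will not be used for this analysis". All secondary analyses are descriptive (SAP 4.10).

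**The concern.** The observation window can be up to 7 days shorter than an eligible woman's normal menstrual cycle. VeraCept is hormone-free, so nothing in the design resets her to a 28-day rhythm. A woman with a long regular cycle can therefore have a 28-day block that starts after one menses ends and finishes before the next begins. Her diary is complete, her menses are normal, and the table records amenorrhea.

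Bleeding and spotting pattern is a named secondary tolerability endpoint. At stake is a row whose percentage would be above zero even if no woman missed a period, with nothing in the table to separate an effect of the window from an effect of the device.

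**Working it through.** The plan states no amenorrhea rate and no sizing for this row, so there is no document figure to reproduce. The question is how often the stated rule labels a normally menstruating woman amenorrheic.

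**Inputs from the documents**
- Window: 28 days, fixed (SAP 4.1.5), anchored on successful insertion (SAP 4.1.2).
- Insertion at any phase of the menstrual cycle (Protocol 12.3).
- Cycle length L: 21 to 35 days (Protocol 8.1, criterion 2).
- Windows in Year 1: 13.

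**Assumption, not in the documents**
- Bleeding or spotting days per menses, b: 3 to 7.

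**Perfectly regular woman.** Number the days of her cycle 0 to L − 1, with bleeding on days 0 to b − 1. A 28-day window starting on day s is empty only if s ≥ b and s + 27 ≤ L − 1. That leaves s from b to L − 28, which is L − b − 27 start days out of L. So

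share of empty windows = max(0, L − b − 27)/L,

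which is above zero only when L ≥ 28 + b. Direct enumeration of all start days agrees for L = 21 to 35 and b = 1 to 8.

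| L (days) | b = 3 | b = 5 | b = 7 |
|---|---|---|---|
| 29–30 | 0% | 0% | 0% |
| 31 | 1/31 = 3.2% | 0% | 0% |
| 32 | 2/32 = 6.2% | 0% | 0% |
| 33 | 3/33 = 9.1% | 1/33 = 3.0% | 0% |
| 34 | 4/34 = 11.8% | 2/34 = 5.9% | 0% |
| 35 | 5/35 = 14.3% | 3/35 = 8.6% | 1/35 = 2.9% |

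With b = 8 or more it never happens in the eligible range. At L = 35 and b = 5 a woman averages 13 × 3/35 = 1.1 empty windows in Year 1, and 15 of the 35 possible start days (42.9%) give at least one.

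**Across a population.** The distribution of L is not given, so two assumptions were tried.
1. L uniform on 21 to 35, each woman perfectly regular. For b = 5 the rate per window is (1/33 + 2/34 + 3/35)/15 = 1.17%. It is 2.97% for b = 3 and 0.19% for b = 7.
2. Simulation with mean cycle 28 to 29 days, between-woman SD 2.5 truncated to 21–35, within-woman SD 1 to 4, b = 5 to 7 and no true amenorrhea. Between about 0% and 2.4% of windows are empty. The top value needs within-woman SD 4, at which many single cycles fall outside 21–35 days. If every individual cycle is held to 21–35 days, the maximum is about 1.1%. Shorter bleeding raises the rate: with b = 3, mean 28 to 30, between-woman SD 2.5 to 3 and within-woman SD 2 (single cycles not restricted), it is 1.5% to 3.8%.

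**Longer window.** A period of W days can be empty for a regular woman only if L − b ≥ W. With L ≤ 35 this cannot occur once W is 35 or more. In the b = 5 to 7 simulations no woman had an empty 91-day period.

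**The case against.** The strongest reply is that this is small and local. The row is descriptive, covers Year 1 only and feeds no test or decision. Amenorrhea appears in neither the protocol's endpoint list (5.2) nor its bleeding analysis (20.7.3). It is one line added in the SAP. All of that stands and limits the weight of the point.

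A reader might also infer more than the documents support:
- *That every woman with a cycle above 28 days is affected.* If any bleeding or spotting day counts, a regular woman with 5 bleeding days and a 29–32 day cycle is never misclassified, and at L = 35 over 91% of her blocks are classified correctly. The wider claim needs a rule based on menses onset, giving (L − 28)/L, from 3.4% at 29 days to 20.0% at 35. The SAP does not state such a rule.
- *That most of the reported percentage would be artefact.* No expected amenorrhea rate is given. Protocol 8.3 allows insertion after a recent pregnancy without two normal menses, so genuine delays are possible. The documents also associate copper devices with intermenstrual bleeding, which would fill some otherwise empty blocks.
- *That parity groups would differ for this reason.* Nothing in the documents says that cycle length varies with parity.
- *That the share of women with at least one empty block measures the bias.* The SAP reports by cycle, so the per-block rate is the relevant figure.

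Finally, the documents do not single out 91 days. That is right: any period longer than 35 days serves regular women, and 91 is a convenient choice.

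**Conclusion.** The point holds in a limited form. The stated rule can tabulate a normally menstruating woman with a complete diary as amenorrheic in a minority of blocks, when her cycle is at least 28 + b days long. For regular women the rate is at most 14.3% of blocks (L = 35, b = 3) and is zero for many eligible cycle lengths. Averaged over women, the false rate is about 0 to 2.4% per block for b = 5 to 7, or up to about 1.1% with all individual cycles inside 21–35 days. These averages rest on assumed bleeding durations and cycle-length distributions; the mechanism itself follows from the documents alone. It affects one descriptive Year 1 tolerability row and leaves the Pearl Index and the pregnancy life table untouched. It is minor, but cheap to put right.

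**What to change.** In SAP 4.12.6:
- State that amenorrhea means no bleeding or spotting recorded in the reference period.
- Report it over a period longer than 35 days, for example four 91-day periods: Days 1–91, 92–182, 183–273 and 274–364. These divide the 364-day Year 1 exactly.
- Add missing-day and early-exit rules scaled to that period, because the present limit of 7 missing days applies to 28.
- Keep the 28-day blocks for the bleeding and spotting day counts.
- If the by-cycle row is kept, label it *no bleeding or spotting in a 28-day window*, not amenorrhea.

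The daily bleeding diary already runs through Month 12, so no new data are needed. The cost is a revised paragraph, a changed table shell, the new missing-day and early-exit rules, and four time points where there are now thirteen.

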13 E-DIARIES

Subjects will be instructed to complete e-diaries daily. Training and detailed instructions on how to complete the e-diary will be provided to subjects. The screening period will be used to train the subjects on how to use the e-diary and to assess the subject's e-diary completion compliance. The diary data collected during the screening period will not be used in the analysis. Subjects will have up to 7 days to input e-diary data for each day. During subject visits and contacts, the site should review the e-diary with the subject to assess for e-diary completion. In addition, all e-diary entries should be reviewed and assessed for adverse

events and concomitant medications. Subjects should be re-educated if they are not completing the diary or are incorrectly completing it. E-diaries are designed to collect the following information for each day of the 28-day cycle from Screening through Month 12:

- Day of cycle
- Date
- Absence or presence of scheduled (menstrual) or unscheduled (intermenstrual)
 vaginal bleeding/spotting (none, spotting, light bleeding, normal bleeding or heavy
 bleeding)
- Vaginal intercourse
- IUD expulsion (yes, no, suspected)
- Usage of additional birth control methods and type of birth control used
- Presence of menstrual pain or cramping
- Adverse events
- Concomitant medications

Vaginal bleeding categories are defined as follows:

- None: no bleeding or spotting
- Spotting: a minimal amount of vaginal bleeding and only one panty liner is used all day or did not use any protection (panty liner, pad, tampon)
- Light bleeding: have vaginal bleeding and one or two pads or tampons are used, or more than one panty liner is used, throughout the day
- Medium bleeding: have vaginal bleeding and three or four pads or tampons are used throughout the day
- Heavy bleeding: have a large amount of vaginal bleeding and more than four pads or tampons are used throughout the day

From Month 13 – Month 96 the following will be collected:

- Day of cycle
- Date
- Vaginal intercourse
- IUD expulsion (yes, no, suspected)
- Usage of additional birth control methods and type of birth control used
- Adverse events
- Concomitant medications

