4.12.7 Subject Discomfort with Study Drug

The occurrence and severity of menstrual pain or cramping will be summarized by cycle for the ECYC population for the first year of treatment.

Only cycles with assessment of bleeding (menstruation) will be included in the analysis.

The analysis will be repeated by parity status at enrollment.

Experience of any menstrual pain or cramping will be recorded daily by the subject in the e-diary in the first year. If menstruation reported is in a cycle, but menstrual pain or cramping is completely missing, then missing values will be imputed as pain or cramping of the maximum intensity.

The following parameters will be reported in the table and data will be presented in the listing:

- Number (%) of subjects with menstrual pain by cycle
- Number (%) of subjects with menstrual pain by maximum severity by cycle
- Number (%) of subjects with menstrual cramping by cycle
- Number (%) of subjects with menstrual cramping by maximum severity by cycle

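### Year 1 bleeding tables keep cycles with unfilled diary gaps of 3 to 7 days, which can only lower the day count and can record false amenorrhea

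*SAP*

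**What the plan says.** **Bleeding (SAP 4.12.6).** The outcome is the number of days, summarised by n, mean (SD), minimum, median and maximum, "in each 28-day cycle with bleeding or spotting, bleeding only, and spotting only". In addition: "Number (%) of subjects with amenorrhea (absence of menstruation) will also be reported by cycle".

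Missing diary days are handled by length of gap:

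- Whole cycle: "If there are more than 7 missing values in a cycle of 28 days, the cycle will not be used for this analysis". A cycle with up to 7 missing days is therefore used.
- One day: "Single missing values will be imputed as the maximum bleeding intensity recorded on the day before and after the missing day".
- Two days: "Two consecutive missing values will be imputed by carrying forward the last non-missing and carrying backward the next non-missing".
- Longer runs: "Three or more consecutive missing will be left missing".

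Nothing is said about how days that remain missing enter the day count or the amenorrhea classification. Protocol section 13 gives subjects up to 7 days to enter each diary day, and the SAP revision history calls this a lockout, so a gap cannot be filled in later.

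**Menstrual pain or cramping (SAP 4.12.7).** If menstruation is reported in a cycle but pain or cramping is wholly absent from the diary, "then missing values will be imputed as pain or cramping of the maximum intensity". The planned tables give maximum severity by cycle, for pain and for cramping separately. In Protocol section 13 the only matching diary item is "Presence of menstrual pain or cramping", with no grade.

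**The concern.** An unfilled run that stays in the analysis contributes nothing to the numerator, while the result is still read as days out of 28. Bleeding that fell in the run is lost, and no bleeding can be added, so the error from these runs has one direction. If the run covers the menses, the cycle has no recorded bleeding and can be tabulated as amenorrheic.

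Bleeding and spotting pattern is a secondary tolerability endpoint (Protocol 5.2, SAP 2.2). The protocol's introduction names increased bleeding and cramping as complaints with an existing copper device. An understated bleeding count would flatter the product on that feature.

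The pain tables raise a separate question. If the diary holds only presence or absence, the severity cells have no listed data source, and the top cell could be populated by the fill alone.

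**Working it through.** The plan states no figure that depends on these rules, so there is none to reproduce. The check follows the SAP rules through a single cycle.

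**Inputs from the documents.** Cycle of 28 days; retained if at most 7 days are missing; runs of 3 or more unfilled. The affected gap lengths are therefore g = 3 to 7.

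**Assumed inputs.** One bleed of L consecutive days (L = 5 as the main case, 3 and 7 as the range) and one gap of g days, each wholly inside the cycle, with all placements equally likely.

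**1. Loss in an affected cycle.** For each of the (29 − L) × (29 − g) placements, loss = L minus the bleeding days outside the gap. Averages:

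| Bleed L | Gap g | Mean days lost | Share of bleed | Whole bleed hidden |
|---|---|---|---|---|
| 3 | 3 | 0.33 | 11% | 3.8% |
| 3 | 5 | 0.56 | 19% | 11.5% |
| 3 | 7 | 0.79 | 26% | 19.2% |
| 5 | 3 | 0.56 | 11% | 0% |
| 5 | 5 | 0.97 | 19% | 4.2% |
| 5 | 7 | 1.38 | 28% | 12.5% |
| 7 | 3 | 0.79 | 11% | 0% |
| 7 | 5 | 1.38 | 20% | 0% |
| 7 | 7 | 2.00 | 29% | 4.5% |

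If placements may wrap round the cycle, the loss is simply g/28: 3/28 = 11%, 5/28 = 18%, 7/28 = 25%. The two conventions agree closely.

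**2. False amenorrhea.** The gap must be at least as long as the bleed and must cover it. For L = 5 and g = 7 there are 24 × 22 = 528 placements. The bleed is hidden when the gap starts 0, 1 or 2 days before it: 20 × 3 + 2 × 2 + 2 × 1 = 66 placements, and 66/528 = 12.5%. With wrapping it is 3/28 = 10.7%. When g < L the probability is zero.

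**3. Short gaps.** Under the same set-up, the one-day rule adds about 0.07 days per gap, because a dry day next to a bleed is filled as bleeding. The two-day rule changes the count by about −0.01 days. The downward error therefore comes from the unfilled runs only.

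**4. Effect on the table mean.** If a fraction f of analysed cycles has such a run, the mean falls by f × loss. The documents give no f. As illustration only, for a 5-day bleed, f = 10% with 3-day gaps gives 0.10 × 0.56 = 0.06 days (1.1%), and f = 30% with 7-day gaps gives 0.30 × 1.38 = 0.41 days (8.3%). The upper end requires nearly a third of all cycles to carry the longest retainable gap.

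**5. Is rescaling a remedy?** Multiplying the count by 28/(28 − g) cuts the mean error for L = 5 from −0.56 to −0.03 days (g = 3) and from −1.38 to −0.18 (g = 7). But menses are clustered. With g = 7 and wrapping, the gap touches the bleed in 7 + 5 − 1 = 11 of 28 placements and misses it in 17/28 = 61%. In those cycles a correct count of 5 becomes 5 × 28/21 = 6.7. That distorts the SD, median and maximum, and a zero count stays zero.

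**6. Pain fill.** Let m be the share of analysed cycles with menstruation reported and pain wholly missing, and q the true maximum-severity share. The reported share is q(1 − m) + m. With q = 10% (assumed), m = 5%, 10% and 20% give 14.5%, 19% and 28%. Neither q nor m is in the documents.

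**The case against.** A reader might infer that the SAP counts every missed day as no bleeding. It does not say so. One-day gaps are filled upward, two-day gaps roughly neutrally, and cycles with more than 7 missing days are removed. Where this SAP wants a missing entry to mean no, it says so, as for intercourse in SAP 4.1.5. One could also argue that a programmer might set the affected cycles aside, or that the bleeding-data recommendations cited in 4.12.6 deal with the point. The first does not sit well with 4.12.6, which defines when a cycle is not used, and these cycles do not meet that test. The second cannot be checked from the documents; in any case the SAP should carry the rule.

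A reader might also infer that the bleeding tables as a whole are biased in the product's favour by a known percentage. The documents do not support that. There is no missingness rate, one-day fills push the other way, and the net sign depends on the mix of gap lengths. What stands is narrower: within retained cycles, an unfilled run has a one-directional effect.

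On pain, the fill is narrower than it may look. It needs menstruation reported and pain entirely absent in that cycle. It is an openly stated worst-case choice, consistent with SAP 4.1.10.6 (missing severity taken as severe) and 4.1.11. Replacing it with an observed-data primary table would be largely preference. The SAP was also written against protocol version 3.0, while the diary list quoted here is from version 7.0, so the diary may hold more than that list shows. The mismatch between the two documents still has to be resolved.

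Finally, these are descriptive secondary summaries in a single-arm study, with no test or threshold attached.

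**Conclusion.** The point holds for retained cycles with an unfilled run of 3 to 7 days. Followed as written, SAP 4.12.6 undercounts bleeding days in those cycles whenever the run overlaps bleeding, and records false amenorrhea when the run covers the whole bleed. For a 5-day bleed and a randomly placed gap, the average loss in an affected cycle is about 11-28%, and a 7-day gap produces false amenorrhea in about 11-13% of placements. These figures assume one bleed, one gap and random timing; gaps that tend to coincide with menses would do more harm. The effect on the reported tables cannot be sized from the documents.

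The secondary point is a mismatch of data source: the SAP plans severity tables and a maximum-intensity fill for an item that the protocol lists as presence only.

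This is a minor matter that leaves the primary endpoint untouched, but it is cheap to settle before analysis.

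**What to change.** **SAP 4.12.6.** Add that, after the one- and two-day fills, a cycle with an unfilled run of 3 or more days is non-evaluable for amenorrhea and is left out of the day-count summaries. Report the number of cycles excluded for this reason, by cycle. Apply the exclusion whether or not bleeding was seen on the observed days: dropping only the zero-count cycles would leave the amenorrhea denominator selectively filled. Do not use 28/observed-day scaling for the reported distribution.

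**SAP 4.12.7.** Reconcile the severity tables with what the diary collects. If only presence is recorded, tabulate presence; if a grade is recorded, list it in Protocol section 13. Beside the worst-case fill, show the observed-data results and the number of imputed cycles.

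**Cost.** SAP wording, simple programming and a few extra table rows; no new data. Slightly fewer cycles contribute to the bleeding summaries. Exclusion also assumes that diary lapses are unrelated to bleeding, which the reported exclusion counts will help readers judge.
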